4.4.3 Study Endpoints

The primary safety endpoint is freedom from major adverse events (MAE) at 30 days or during hospitalization if this exceeds 30 days.

Major adverse events include death, bowel ischemia, myocardial infarction, paraplegia, renal failure, respiratory failure, and stroke.

The primary effectiveness endpoint is the proportion of the study subjects with treatment success at 1 year. Treatment success is defined as a composite of technical success and freedom from the following:

- Aneurysm enlargement i.e., $\geq 5\text{mm}$ as compared to any previous CT measure using orthogonal (i.e., perpendicular to the centerline) measurements
- Aneurysm rupture
- Aneurysm-related mortality
- Conversion to open repair
- Secondary intervention for migration, Type I and III endoleaks, device integrity failure (e.g., fracture), and patency-related events (i.e., device component stenosis or occlusion and embolic events)

Secondary endpoints include:

- Technical success and the individual components of technical success:
 - Successful delivery
 - Deployment at the intended implantation site
 - Patency of all endovascular graft and stent components
 - Absence of device deformations requiring unplanned placement of an additional device
 - Absence of inadvertent covering of aortic branch vessels
 - Successful withdrawal
- Freedom from the individual components of the primary safety endpoint at 30 days:
 - Death
 - Bowel ischemia
 - Myocardial infarction
 - Paraplegia
 - Renal failure
 - Respiratory failure
 - Stroke
- Freedom from paraparesis at 30 days
- The following at each follow-up interval:
 - Treatment success and the individual components of treatment success including freedom from the following:
 - Aneurysm enlargement
 - Aneurysm-related mortality

- Aneurysm rupture
- Conversion to open repair
- Secondary intervention for migration, type I and III endoleaks, device integrity failure (i.e., fracture), and patency-related events (i.e., device stenosis or occlusion and embolic events).
- Renal failure
- All-cause mortality
- Endoleaks
- Device integrity failure (e.g., fracture)
- Patency-related events (i.e., device stenosis or occlusion and embolic events)
- Other device-related events

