3.2 Pathophysiology

Aortic aneurysm is a progressive disease characterized by structural deterioration, gradual expansion, and eventual potential for rupture of the aorta if left untreated. The definition of aortic aneurysm is a localized or diffuse dilatation encompassing all three layers of the aorta with diameter >50% larger than the expected normal aortic diameter.

An aneurysm which spans both the thoracic and abdominal cavities defines a thoracoabdominal aortic aneurysm. The expansion rate of thoracoabdominal aneurysms ranges from 2-4mm per year and is not influenced by the size of the aneurysm at the time of diagnosis^{4,5}. The expansion rate of thoracoabdominal aneurysms does not appear to increase as individual aneurysms enlarge. The presence of COPD and hypertension are factors associated with an increased rate of enlargement^{6,7}. Thoracoabdominal aortic aneurysms become a risk for rupture if they are above 5.5-cm in diameter or if they are less than 5.5-cm in diameter and are growing more rapidly than 0.5-mm in 6 months. The 5-year survival of thoracoabdominal aneurysm patients ranges from 7-20% depending on the percentage of aneurysms secondary to aortic dissection^{5,8}. Half of the thoracoabdominal aneurysm deaths are attributed to rupture and the other half are due to some sort of comorbidity such as myocardial infarction. The overall survival of thoracoabdominal aortic aneurysm patients is often overestimated, because the patients with advanced comorbid medical illness are not included and account for 46-68% of the patients reported in past natural history studies^{5,8-11}. Dissecting aneurysms have a higher rate of rupture and have a worse prognosis without intervention.

Most patients with a descending thoracic or thoracoabdominal aneurysm do not have symptoms when first diagnosed^{9,12}. They are likely diagnosed with a CT scan for another disease. Some patients have vague chest, back, flank, or abdominal pain. The pain may increase in severity as the aneurysm enlarges, or it may be sudden due to rapid expansion and impending rupture. Symptoms can result from compression of or erosion into adjacent intra-thoracic structures or bony thorax^{9,13,14}. Hoarseness from stretching or compression of the left recurrent laryngeal nerve, tracheal deviation, persistent cough, or other respiratory symptoms is sometime

seen. Patients with a thoracoabdominal aortic aneurysm may have a palpable pulsatile mass in the upper abdomen.

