4.4 Protocol

This study is a prospective, single-center, non-randomized, multi-arm study to evaluate the therapeutic benefit of the Valiant™ Thoracoabdominal Stent Graft System. A total of 15 patients will be enrolled in this study.

- 6 subjects total will be treated in the primary study arm
- 9 subjects total will be treated in the expanded selection arm

The duration of the Investigation is anticipated as follows:

- Time to Complete Enrollment: 24 months
- Subject Follow-up Time: 5 years from last subject enrollment
- Total Duration Time: 7 years

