4.4.2 Eligibility Criteria

Primary Study Arm

Inclusion Criteria

- A patient may be entered into the study if the patient has at least one of the following:
 - An aneurysm with a maximum diameter of ≥ 5.5 cm or 2 times the normal diameter just proximal to the aneurysm using orthogonal (i.e., perpendicular to the centerline) measurements
 - Aneurysm with a history of growth ≥ 0.5 cm in 6 months
 - Saccular aneurysm deemed at significant risk for rupture
 - Symptomatic aneurysm greater than or equal to 4.5 cm
- Axillary or brachial and iliac or femoral access vessel morphology that is compatible with vascular access techniques, devices or accessories, with or without use of a surgical conduit

- Proximal landing zone for the thoracic bifurcation stent graft that has:
 - ≥ 2.5 cm of nonaneurysmal aortic segment including previously placed graft material (neck) distal to the left subclavian artery (LSA) and a diameter in the range of 26-42 mm
 - Adequate distance from the celiac artery, in order to accommodate cannulation from the antegrade access point when considering the total deployed length of the thoracic bifurcation and visceral manifold
- Iliac artery or aortic distal fixation site, including both native tissue and previously placed graft, greater than or equal to 15 mm in length and diameter in the range of 8 – 25 mm
- Age: ≥ 18 years old
- Life expectancy: > 1 year

Exclusion Criteria

General exclusion

- Patient is a good candidate for and elects for open surgical repair
- Can be treated in accordance with the instructions for use with a legally marketed endovascular prosthesis
- Is eligible for enrollment in a manufacturer-sponsored IDE at the investigational site
- Unwilling to comply with the follow-up schedule
- Inability or refusal to give informed consent

- Urgent or emergent presentation
- Patient is pregnant or breastfeeding
- Patient has a contained rupture
- Patient has a ruptured aneurysm
- Patient has a dissection in the portion of the aorta intended to be treated
- Obstructive stenting of any or all of the visceral vessels
- Poor performance status including two major system failures (including but not limited to cardiovascular, pulmonary, renal, hepatobiliary, and neuromuscular)
- Prior aneurysm repair that would involve relining of the previously placed graft material requiring placement of the investigational system in a landing zone that expands beyond any limits of the previously placed graft material

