4.4.7 Data Presentation and Analysis Plan

The primary purpose of this study is to evaluate the safety of this device as there are no or very limited devices and clinical options available for this patient population. The primary safety endpoint of this study is freedom from major adverse events (MAE) at 30 days or during hospitalization if this exceeds 30 days. Major adverse events include death, bowel ischemia, myocardial infarction, paraplegia, renal failure, respiratory failure, and stroke. The primary safety endpoint will be analyzed to determine statistical significance when compared to a target performance goal. A literature review of outcomes of open surgical repair was used to create the performance goal as there is not a comparable endovascular option to use for analysis. The performance goal was selected based on the range of subjects experiencing a major adverse event at 30 days. The range was calculated based on assumptions of the minimum and maximum number of subjects experiencing at least one MAE in the historical open surgical repair group (Table 6). Based on the literature reviewed and the above assumptions the range of subjects experiencing at least one MAE in the open surgical repair group is 30.5% to 77.4%.

The primary effectiveness endpoint is the proportion of the study subjects with treatment success at 1 year. The data will be presented as quality outcomes, with the number of study subjects who experience treatment success compared to the overall patient population.

Additionally, data outcomes from this study will be entered into a common vascular database so that data can be pooled with other PS-IDEs. This would provide consistent reporting across the PS-IDEs. Additionally, the PS-IDEs will be evaluating the same device and endpoints to allow for a pool-ability of data across the sites.

The data will be separated into two separate study arms: primary study arm and expanded selection arm.

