Paraparesis: spinal cord ischemic event resulting in partial neurologic deficit in the lower extremities

Parietal arteries (branches): inferior phrenic, lumbars and middle sacral arteries

Patency: the state of a vessel that has unimpeded flow into and out of the vessel

Proximal landing zone: the aortic fixation site closest to the heart

Proximal fixation length: the aortic fixation site measured from the proximal edge of the graft to the start of the aneurysm

Renal insufficiency: rise in serum creatinine of more than 50% above pre-procedure level which results in a serum creatinine >2.0 mg/dl that does not spontaneously resolve

Technical success:

- successful delivery (i.e., ability to deliver the implant to the intended implantation site, without the need for unanticipated corrective intervention related to delivery);
- successful and accurate deployment, defined as:
 - deployment of the endovascular stent-graft at the intended implantation site;
 - patency of all endovascular graft and stent components; absence of device deformations (e.g., kinks, stent eversion, mal-deployment, misaligned deployment) requiring unplanned placement of an additional device;
 - absence of inadvertent covering of aortic branch vessels; and
- successful withdrawal (i.e., successful withdrawal of the delivery system, without need for unanticipated corrective intervention related to withdrawal)

Thrombus: a blood clot that forms due to injury of a vessel. If the thrombus becomes dislodged and travels it is referred to as an embolus

Treatment success: a composite of technical success and freedom from the following:

- aneurysm enlargement i.e. ≥ 10 -mm as compared to any previous CT measuring orthogonal (i.e., perpendicular to centerline) measurements
- aneurysm-related mortality
- aneurysm rupture

- conversion to open repair
- secondary intervention for migration, type I and III endoleaks, device integrity failure (i.e., fracture), and patency-related events (i.e., device stenosis or occlusion and embolic events)
- Renal failure

Type B – Chronic Dissection: a dissection that takes off distal to the left subclavian artery that is greater than 30 days old

Type B – Subacute Dissection: a dissection that takes off distal to the left subclavian artery that is 15-30 days old

Urgent: An aneurysm requiring repair within 1 week

Visceral arteries (branches): celiac, superior mesenteric, inferior mesenteric, renal arteries

5. Manufacturing Information

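### At 1 year the ≥5 mm enlargement component of treatment success separates sac exclusion poorly from the protocol's own natural growth of 2–4 mm/year; a supportive analysis of diameter change from the same CTs would say more

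*Combined protocol and SAP*

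**What the plan says.** Section 4.4.3 defines the endpoint: "The primary effectiveness endpoint is the proportion of the study subjects with treatment success at 1 year". Treatment success combines technical success with freedom from aneurysm enlargement, rupture, aneurysm-related death, conversion to open repair, and secondary intervention for listed causes. Enlargement is growth of at least 5 mm "as compared to any previous CT measure using orthogonal (i.e., perpendicular to the centerline) measurements". The synopsis and the stand-alone enlargement entry in section 4.9 also use 5 mm. The treatment-success entry in section 4.9 does not: "aneurysm enlargement i.e. ≥ 10 -mm as compared to any previous CT".

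On natural history, section 3.2 states: "The expansion rate of thoracoabdominal aneurysms ranges from 2-4mm per year". Section 4.4.2 lists, as one of four alternative routes into the study, "Aneurysm with a history of growth ≥ 0.5 cm in 6 months".

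On analysis, section 4.4.7 says: "The data will be presented as quality outcomes, with the number of study subjects who experience treatment success compared to the overall patient population". The arms (6 and 9 subjects) are shown separately. No null value, test or performance goal is set for effectiveness, and no analysis of diameter as a continuous measure is listed. Section 4.4.3 does list treatment success and its components at every follow-up interval. Section 4.4.5.6 schedules CTA at each visit where renal function permits.

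**The concern.** The enlargement component is a yes/no reading with its cut-off above the growth that the protocol itself expects in one year without repair. A sac that had not been excluded, but grew at the average rate, would usually count as free from enlargement at month 12. A subject who entered because of one fast 6-month interval and then returned to 2–4 mm/year would also pass without any device effect.

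Sections 4.4.6 and 4.4.7 say that the data will be pooled with other physician-sponsored studies, and section 4.4.6 that they should support the design of a pivotal study. If a high 1-year proportion is read as evidence that the sac was excluded, that design inherits an overstated effect. The CTs already scheduled hold more information than the yes/no reading uses.

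**Working it through.** **Inputs from the documents.** Growth 2–4 mm/year (3.2); failure line 5 mm (4.4.3) or 10 mm (treatment-success entry, 4.9); CT before operation and at months 1, 6 and 12 (4.4.4, Table 5); 15 subjects, 6 and 9 by arm (4.4). There is no planned figure for this component to reproduce.

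**Assumptions.** Growth rate g uniform on 2–4 mm/year; independent normal error on each CT with SD σ = 0.5, 1.0, 1.5 or 2.0 mm. The documents give neither a distribution nor an error.

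**Step 1: no measurement error.** Growth by month 12 is 2–4 mm, below 5 mm. Every sac in the stated range passes.

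**Step 2: month 12 against month 1.** Expected growth is (11/12) × 2 to (11/12) × 4 = 1.83 to 3.67 mm, mean 2.75 mm. The pass probability is Φ((5 − 11g/12)/(√2·σ)), averaged over g. At σ = 1.5 and g = 3 this is Φ(2.25/2.12) = Φ(1.06), about 86%; averaging over g gives 85%.

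**Step 3: the written rule.** Simulation with CTs at months 0, 1, 6 and 12, failing on any rise of 5 mm or more over any earlier CT.

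| CT error SD (mm) | Growing sac passes, month 12 vs 1 | Growing sac passes, any previous CT | Stable sac passes, any previous CT |
|---|---|---|---|
| 0.5 | 99.6% | 98% | 100% |
| 1.0 | 93% | 86% | 99.9% |
| 1.5 | 85% | 69% | 95% |
| 2.0 | 78% | 54% | 83% |

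Other readings of the rule fall between the first two columns. Month 12 against any earlier CT gives 98, 86, 72 and 62%. Postoperative CTs only give 99.6, 93, 80 and 69%. At the 10 mm line a growing sac passes at least 98% of the time in every case.

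The written rule fails more growing sacs than the month-1 comparison, but part of that is noise: a sac with no growth at all fails 5% of the time at SD 1.5 mm and 17% at SD 2.0 mm.

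**Step 4: what a perfect count shows.** The exact two-sided 95% lower bound for n of n is 0.025^(1/n): 78.2% for 15/15, 66.4% for 9/9 and 54.1% for 6/6. At σ = 1.5 the chance that naturally growing sacs all pass is 0.85^15 ≈ 8% and 0.85^6 ≈ 37% for month 12 against month 1. Under the written rule it is 0.685^15 ≈ 0.3% and 0.685^6 ≈ 10%.

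**Step 5: the same CTs as a change.** At σ = 1.5, the between-sac SD of growth is 2/√12 = 0.58 mm/year. The SD of the 11-month change is √(2 × 1.5² + (0.58 × 11/12)²) = 2.19 mm. The 95% half-widths are:

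- n = 15: 2.145 × 2.19/√15 = 1.2 mm
- n = 9: 2.306 × 2.19/√9 = 1.7 mm
- n = 6: 2.571 × 2.19/√6 = 2.3 mm

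An observed mean change of zero would exclude the whole range of 1.83–3.67 mm at n = 15, and just do so at n = 9. At n = 6 it would exclude the middle of the range but not its lower part. With a true mean of zero at n = 6, the upper limit falls below 1.83 mm with probability about 38%, and below 2.75 mm about 69%. At σ = 2.0 the n = 6 half-width is 3.0 mm.

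As a direct comparison at n = 15, one-sided 2.5%, take a treated mean change of 0 against natural growth of 3 mm and one baseline-to-12-month change per subject. With an assumed SD of change of 3 mm, power is 95% for the mean change and 48% for the yes/no reading. At SD 5 mm it is 58% and 29%.

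**The case against.** A reader might infer that a repair with no effect would reach treatment success anyway, so that even 15 of 15 would show nothing. The documents do not support that.

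- **It is a composite.** Rupture and aneurysm-related death also count. Section 3.2 gives 5-year survival of 7–20%, with half of deaths from rupture. At an assumed constant hazard, 1-year survival is 0.07^(1/5) = 59% to 0.20^(1/5) = 72%, so rupture death by 1 year is half of 41% to 28%, about 21% to 14%. An untreated group would fail the composite more often than the enlargement component alone suggests.
- **The reference CT matters.** Under the written rule at SD 1.5 mm, a no-effect 15/15 on this component has probability about 0.3%, against 8% for month 12 versus month 1. The comparison with 2–4 mm/year also describes the average: a subject who kept growing at 5 mm or more per 6 months would fail.
- **No planned test fails.** Effectiveness is presented descriptively in a small feasibility study.
- **Part of the remedy exists.** Section 4.4.3 already reports the components, and endoleaks, at every interval, so a 24- and 36-month display is planned. Table 8 already counts subjects with paired size data.

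All four stand, and they limit the point to interpretation of one component. They do not supply an analysis of diameter change, and they do not remove the overlap between a stable and a naturally growing sac at the 5 mm line.

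**Conclusion.** The point holds for the enlargement component at 1 year. The protocol's own average growth lies below the 5 mm line, and far below 10 mm. The no-effect pass rate is about 99.6–78% (month 12 against month 1) or 98–54% (any previous CT), resting on uniform growth of 2–4 mm/year and assumed CT error SDs of 0.5–2.0 mm; it is not a figure that the protocol itself yields. The harm is to how a high success proportion is read and carried into pivotal planning.

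A reader might also infer that analysing change is bound to exclude natural growth. It could, but this is not assured. The SD of change in treated sacs is not in the documents, and the 6-subject arm is weak. This is a cheap improvement rather than a flaw that invalidates a planned inference.

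**What to change.** 1. Reconcile the 10 mm in the treatment-success entry of section 4.9 with the 5 mm in the synopsis, section 4.4.3 and the stand-alone definition. Keep growth of at least 5 mm as the failure event.
2. In section 4.4.7 add a supportive analysis: change in maximum orthogonal diameter from a named reference CT, the first after the repair is complete, to month 12. Show it by arm and overall, as a mean with 95% CI beside 2–4 mm/year scaled to the interval, with counts of shrinkage of at least 5 mm, stable, and growth of at least 5 mm. Give the number of subjects with both CTs.
3. State that freedom from growth of 5 mm or more at 1 year is not by itself evidence of exclusion.

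**Cost.** A little analysis on CTs already scheduled, with no added scans or subjects, and a more cautious 1-year statement. Some CTs will be missing after death or where renal function does not allow them. In staged repairs, where completion is targeted at 4–6 weeks, the first scheduled CT after completion may be month 6. The interval is then 6 months and expected natural growth only 1–2 mm.

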3.4.2.1 Staged Procedures

With the Valiant Thoracoabdominal stent graft system, the risks of planned staging via the visceral artery bridge endoleak during the procedure are comparable to the single stage procedure in the current protocol. We do not believe staging presents any new risks that are not currently covered under the risk profile for the VTAAA system, but these risks may happen at a higher frequency. These risks still present no greater risk than the probable risk from the progression of the patient's condition. The increased risks for a planned stage procedure (visceral artery bridge endoleak or delayed distal seal) are risks from an additional procedure including anesthetic and contrast exposure, compounded physiologic insult from multiples procedures, access site complications, wire injury, device integrity issues from component interaction, paraplegia, spinal cord ischemic event, aneurysm enlargement, aneurysm rupture, and death. Increased risks for a bail-out staged procedure include the above risks and increased procedure time or failure to treat.

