Completion of the staged procedure is targeted for 4-6 weeks following the index procedure, but will be based on physician discretion, clinical presentation, and patient compliance.

Note: The physician may choose to complete the procedure earlier if the patient is symptomatic or has other concerns for aneurysm sac growth or rupture.

Completion procedure may be performed under local or general anesthesia. Vascular access will be established in the brachial or axillary

artery. The staged limb of the visceral manifold will be cannulated and the bare segment will be covered over by at least one iCast.

b. Planned Stage Procedure: Delayed distal seal

i. This refers to completing the visceral debranching (manifold to target arteries) with covered stents and subsequently leaving out one or more of the distal aortic/iliac components.

ii. Device Visualization and Preparation

Refer to the Instructions for use provided for the distal aortic/iliac components to be used.

iii. Distal Aortic/Iliac Component Deployment

Follow the study protocol or IFU for deploying the distal aortic/iliac components.

iv. Completion

Completion of the staged procedure is targeted for 4-6 weeks following the index procedure, but will be based on physician discretion, clinical presentation, and patient compliance.

Note: The physician may choose to complete the procedure earlier if the patient is symptomatic or has other concerns for aneurysm sac growth or rupture.

Completion procedure may be performed under local or general anesthesia.

c. Bail-out Stage Procedure

- i. A bail-out method may be used for staging in the event patient status declines during the case or inability to technically complete the case.
- ii. Device Visualization and Preparation
Refer to the Instructions for use provided for the components to be used.
- iii. Device Deployment
Refer to the Valiant™ Thoracoabdominal Stent Graft System (IFU) for device deployment and implantation of the remaining components.
- iv. Completion due to patient status decline
Completion of a bail-out staged procedure due to patient status should be completed as soon as clinically feasible following the index procedure, but will be based on physician discretion, clinical presentation, and patient compliance.
- Note: The physician may choose to delay staging if the patient has complications or there are concerns with completing the secondary procedure.*
- v. Completion due to inability to technically complete the case

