Completion of a bail-out procedure due to technical challenges have the following options that present no more risk than the alternative of no treatment.
 - a. Complete case at another date
 - b. Medical management
 - c. Convert to open surgical repair

- d. Referral to another facility/investigator that can complete the procedure

Note: Caution should be taken when relining previously placed graft material to prevent complications from graft on graft friction including decreased graft maneuverability and challenges repositioning.

Note: For proximal extension of the thoracic bifurcation, two Valiant Captivia or Valiant Navion thoracic grafts can be used. One to extend the landing zone more proximally and one to layer to prevent wear. Deploy the Valiant Captivia or Valiant Navion thoracic grafts according to their respective manufacturer's IFU and continue according to the implant procedures the Medtronic Valiant Thoracoabdominal Stent Graft System IFU.

Note: For type 1 and 5 aneurysms the distal end of visceral bypass (VB) should be sized to provide the distal seal with the aorta and then proceed to Step 4.4.5.5, Completion Procedures. For type 2 and 3 proceed to deployment of the infrarenal bifurcation and Endurant II limb stent graft instructions in the Medtronic TAAA Debranching Stent Graft System IFU.

Note: If the VB is too short or too small to provide distal seal, a Valiant Captivia stent graft or Endurant Limb may be used in place or in conjunction with the Visceral Bypass to provide adequate distal seal. For type 2 and 3 proceed to deployment of the infrarenal bifurcation and Endurant II limb stent graft instructions in the Medtronic TAAA Debranching Stent Graft System IFU. If a commercially available Endurant limb or Valiant stent graft is used as the Visceral Bypass a commercially available Endurant

mainbody stent graft with suprarenal fixation and a Gore cuff is required for adequate fixation. See Step 1.4.5.5.3.C and Step 1.4.5.5.4.D. below for deployment procedures.

Note: If treating a subject with an occluded visceral vessel, a vascular plug may be used to occlude the extra limb of the TAAA Visceral Manifold stent graft.

B. Surgical Decision Pathway and Bailouts

[figure not shown]

Figure 4: Surgical decision path and possible bailouts

C. Visceral Bypass (VB) Instructions (Endurant Long Limb)

1. Insert a guidewire from the groin through the 16-mm limb of the thoracic bifurcation.

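### Treatment success has no component for completing the repair, so a staged subject who is never completed can be scored a 1-year effectiveness success

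*Combined protocol and SAP*

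**What the plan says.** Section 4.4.3 (repeated in the synopsis) defines the primary effectiveness endpoint as the proportion of subjects with treatment success at 1 year: "Treatment success is defined as a composite of technical success and freedom from the following". The listed events are aneurysm enlargement of 5 mm or more, rupture, aneurysm-related mortality, conversion to open repair, and "Secondary intervention for migration, Type I and III endoleaks, device integrity failure (e.g., fracture), and patency-related events". Section 4.9 restates the definition with a 10 mm enlargement threshold and adds renal failure.

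Technical success (section 4.9) requires:
- "successful delivery (i.e., ability to deliver the implant to the intended implantation site, without the need for unanticipated corrective intervention related to delivery");
- "deployment of the endovascular stent-graft at the intended implantation site";
- patency of the components, no deformation needing an unplanned device, no inadvertent branch coverage, and successful withdrawal.

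Section 4.4.5.3 allows the repair to be left open in three ways:
- **Visceral artery bridge endoleak (planned).** A short bare segment is left in a bridge so that the sac stays perfused, and it is covered in a later procedure.
- **Delayed distal seal (planned).** One or more distal components are left out at the index procedure.
- **Bail-out.** "A bail-out method may be used for staging in the event patient status declines during the case or inability to technically complete the case".

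Planned completion has a 4-6 week target that yields to the surgeon's judgement and the patient's condition and adherence. No latest date is given. For technical inability the text says: "Completion of a bail-out procedure due to technical challenges have the following options that present no more risk than the alternative of no treatment". The options are another date, medical management, open conversion, or referral. Section 3.4.2.1 lists "increased procedure time or failure to treat" among the added risks of bail-out staging.

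**The concern.** The endpoint is meant to show that the device repairs the aneurysm. Every listed component is either a property of the implant procedure or the absence of a later event; none says that the repair was finished. Endoleak enters the composite only through a secondary intervention, so a leak left deliberately and never closed is not in itself a failure.

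The protocol creates this situation by design. Table 9 in section 4.7 counts a subject as enrolled once the device enters the body, so staged and bailed-out subjects are in the study population and must be scored. If non-completion can pass, the reported proportion mixes excluded aneurysms with unexcluded ones. Sections 4.4.6 and 4.4.7 say that the data will be pooled with other physician-sponsored IDEs and used to develop a pivotal study, so the ambiguity would carry forward. A rule written after outcomes are known would be post hoc.

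**Working it through.** No stated figure in the plan rests on this endpoint, so there is none to reproduce. The check sets the definitions against the staging text, followed by simple arithmetic.

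**Step 1. Score each type of subject, assuming no completion by 12 months and no listed event.**

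| Subject | Technical success (4.9) | Listed events (4.4.3) | Score as written |
|---|---|---|---|
| Planned bridge endoleak | Index components delivered, placed and patent as intended: no item fails | None | Can be a success |
| Planned delayed distal seal | Same; the missing components were not intended at the index procedure | None | Can be a success |
| Bail-out for clinical decline, all opened components well placed | No item clearly fails | None | Can be a success |
| Bail-out for technical inability, then medical management or referral | Delivery or deployment may already fail; the text does not settle it | None | Ambiguous |
| Bail-out, then open conversion | Not needed | Conversion | Failure |

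The last row breaks the no-event assumption and is shown for contrast. Of the four options after technical inability, open conversion is the only one that is itself a listed failure.

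**Step 2. Does the enlargement component catch non-completion?** Section 3.2 states: "The expansion rate of thoracoabdominal aneurysms ranges from 2-4mm per year". Time to threshold = threshold / growth rate.
- 5 mm (section 4.4.3): 5/4 = 1.25 years (15 months) to 5/2 = 2.5 years (30 months).
- 10 mm (section 4.9): 10/4 = 2.5 years (30 months) to 10/2 = 5 years (60 months).

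Growth over 12 months is 2-4 mm, below both thresholds. Two qualifications apply. The comparison is with any earlier CT, so at 4 mm per year a baseline scan taken 3 months before implant would give 15 months of growth, or 5 mm, at the 12-month visit. Section 4.4.2 also admits patients on growth of at least 0.5 cm in 6 months; if that rate continued, the sac would reach 5 mm at 6 months and 10 mm at 12 months and would fail under either threshold.

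**Step 3. Weight of one subject.** Arm sizes come from section 4.4. The change in the proportion is 1/n. Intervals are exact (Clopper-Pearson) 95%. The documents give no number of never-completed subjects, so the counts below are assumptions for illustration.

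| Group | Shift per subject | All successes | One rescored | Two rescored |
|---|---|---|---|---|
| Primary, n=6 | 1/6 = 16.7 points | 6/6 = 100% (54-100) | 5/6 = 83% (36-100) | 4/6 = 67% (22-96) |
| Expanded, n=9 | 1/9 = 11.1 points | 9/9 = 100% (66-100) | 8/9 = 89% (52-100) | 7/9 = 78% (40-97) |
| All, n=15 | 1/15 = 6.7 points | 15/15 = 100% (78-100) | 14/15 = 93% (68-100) | 13/15 = 87% (60-98) |

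**Step 4. Does anything inferential change?** No. Section 4.4.7 presents effectiveness as a descriptive proportion with no goal or test. The 50% performance goal, the one-sided 2.5% level and the pooled sample size of 46 in section 4.4.7.1 belong to the 30-day safety endpoint.

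**The case against.** The strongest reply is that the composite still catches most bad outcomes. An unfinished subject fails on rupture, aneurysm-related death, open conversion, enlargement past the threshold or a qualifying secondary intervention. A bail-out for technical inability may already fail delivery or deployment. The 2-4 mm range describes natural history, while section 3.4.2.1 lists enlargement and rupture among the raised risks of staging. Endoleak is a secondary endpoint at every visit, and the interim reports in section 4.7 describe additional interventions and procedural success, so a perfused sac would not be hidden. The endpoint is descriptive, in a 15-subject feasibility study.

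All of this limits the point, but none of it supplies the missing component. A secondary endpoint does not change how the primary one is scored.

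A reader might infer more than the documents support:
- *Every unfinished repair counts as a success.* The text supports only that it can, given no listed event.
- *Non-completion runs at about 2 in 6.* Section 3.5.1 reports 6 staged cases, 4 excluded and 2 awaiting completion. That is a snapshot of pending cases with no time since the index procedure. It shows that open stages occur and is not a rate at 12 months.
- *The overstatement is worst in the expanded arm.* Section 4.4.5.3 leaves staging to the surgeon without reference to arm.
- *The bias can only be upward.* The plan does not say whether a planned completion is a secondary intervention for endoleak. If it were read that way, a properly completed subject would be scored a failure and effectiveness would be understated.

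**Conclusion.** The point holds in a limited form. As written, a planned-staged subject, or one bailed out for clinical decline with all opened components well placed, can be a 1-year effectiveness success with the aneurysm not excluded. This requires that the repair is never completed and that no listed event occurs. Bail-out for technical inability that ends in medical management or referral is left unclassified. Enlargement cannot be relied on to catch these subjects at the protocol's own growth range, although faster-growing sacs would fail.

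The per-subject shifts are the weight of any one subject, not an estimate of how many will be misclassified; that number is unknown. The conclusion rests on reading technical success against what was intended at the index procedure, a reading the definitions permit but do not state. The effect is confined to the reported proportion and to what is pooled from it.

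**What to change.** In sections 4.4.3 and 4.9:

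1. Add a component to treatment success: *repair completed by the 12-month visit, meaning all planned or bail-out stages done, each intended target vessel connected or its limb closed as planned, and distal seal made.*
2. Score a subject not completed by then as a failure, including those referred elsewhere or moved to medical management.
3. State that a planned stage completion is not a secondary intervention for endoleak. Without this, a staged subject could fail whether completed or not.
4. Report the number of non-completions by arm.

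While editing, reconcile the enlargement threshold (5 mm or 10 mm) and the renal failure item between the two sections.

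This changes endpoint scoring only, not when or how stages are performed. It also does not address an untreated Type I or III leak in a completed repair, which stays visible through the endoleak secondary endpoint.

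The cost is small: endpoint wording, a possibly less favourable success proportion, and outside records for referred subjects. For the rest, operative records and scheduled CT largely supply the data. The rule should be set before 1-year outcomes are scored.
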